12.0 CRITERIA FOR EVALUATION/REMOVAL FROM STUDY

Every subject should be encouraged to remain in the study. Possible reasons for early withdrawal may include, but are not limited to, the following:

1. Withdrawal of consent – Subject decides to withdraw from the study. This decision must be an “independent decision” that is documented in the source documentation.

2. Principal Investigator and/or treating physician discretion – The Principal Investigator and/or treating physician may choose to withdraw a subject from the study if there are safety or other concerns.
3. Subject becomes pregnant.
4. Subject non-compliance.
5. Subject lost to follow-up.
6. Subject death.

13.0 STATISTICAL METHODS

13.1 General Considerations

Statistical analysis of this study will be the responsibility of the Department of Biostatistics at Indiana University School of Medicine. Parameter estimates and relevant summary statistics will be reported for both efficacy and safety outcomes. Continuous variables will be summarized by means, medians, minima, maxima and standard deviations. Categorical variables will be summarized by frequencies and percentages. Missing data will not be imputed. Additional exploratory analysis will be conducted when appropriate. Changes from the analysis plan will not require an amendment to the protocol unless it changes a significant feature in the protocol. The statistical analysis methods are outline below.

13.2 Study Design

This is a pilot non-randomized study.

13.3 Analysis Population

13.3.1 Enrolled Population

The enrolled population comprises all subjects who meet the eligibility criteria and are registered onto the study.

13.3.2 Safety Population

The safety population comprises all subjects who have received at least one dose of radiation. This set will be used for safety analysis.

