5.0 ELIGIBILITY CRITERIA

5.1 Inclusion Criteria

1. Subjects must be ≥ 18 years of age at the time of signing informed consent
2. Diagnosis of primary liver malignancy (including hepatocellular carcinoma [HCC] or cholangiocarcinoma) or liver metastasis from any primary solid tumor site by characteristic imaging findings on CT or MRI, clinical presentation, and/or pathologic confirmation of diagnosis. Subjects with other current or prior malignancies are eligible for this study.
3. Patients with liver metastases must have at least one of the following clinical factors that may affect liver function:
 - a. History of liver resection (at any time)
 - b. History of cirrhosis (any cause), fatty liver disease, or hepatic insufficiency due to any cause
 - c. Prior radiation to the upper abdomen including radioembolization
4. ECOG (Zubrod) Performance Status 0-2.
5. Subjects must have a Child-Turcotte-Pugh (CTP) score ≤ 7 to be eligible.
6. Patients who have been previously treated with non-SBRT liver directed therapies may be enrolled on study. At least 3 months must have elapsed between the most recent liver-directed therapy and study entry.
7. Ability to provide written informed consent and HIPAA authorization
8. Subjects with an allergy to contrast agents may be enrolled at the treating physician's discretion with appropriate pre-treatment and symptom management.

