9.2 Research Imaging Protocols

1. HIDA scan
2. MRI with Eovist contrast of abdomen and pelvis

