13.7 Analysis of Secondary Objectives

The rate at which the plan that utilized the HIDA scan is chosen for the actual treatment will be summarized along with the corresponding exact 95% Binomial confidence interval.

For Local Control, PFS, OS, time to transplant, time to distant liver failure, and time to salvage treatment, the median and the corresponding two-sided 95% confidence intervals will be calculated using the Kaplan-Meier method. Estimates and 95% confidence intervals will also be provided for 6 and 12 months. Local control will be evaluated using RECIST 1.1 criteria.

Changes in liver function tests using HIDA scans, standard blood tests and CTP score will be calculated and summarized. Additionally, all safety data will be listed. For the treatment-emergent AEs, namely AEs started or worsened during the on-treatment period, the incidence will be summarized by system organ class and/or preferred term, severity based on CTCAE grades, type of adverse event and the relation to the study drug. Deaths reportable as SAEs and non-fatal serious adverse events will be listed by and tabulated by type of adverse event. This will be done with the safety set.

Changes in liver volume in the treated and untreated segments will be summarized by basic summary statistics.

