17.3 Adverse Event (AE) and Serious Adverse Event (SAE) Reporting

Adverse events (AEs) will be recorded from the time of first study intervention and throughout the follow up period. All AEs considered related to the study intervention will be followed until resolution, return to baseline, or deemed clinically insignificant, even if this occurs post-study. Any death occurring within 30 days after the last study intervention must be reported as an SAE regardless of attribution.

17.3.1 Reporting to the IRB:

1. Unanticipated problems involving risks to subjects or others will be reported promptly to the IRB if they:
 - Unexpected;
 - Related or possibly related to participation in the research; and
 - Suggests that the research places subjects or others at a greater risk of harm than was previously known or recognized.

If the serious adverse event does not meet all three (3) criteria listed above, the event does not have to be promptly reported to the Indiana University IRB. However, it should be reported at the time of continuing review

2. Prompt reporting of unanticipated problems to the IRB is defined as within 5 days from becoming aware of the event.

17.3.2 Reporting to the Data Safety Monitoring Committee (DSMC):

Regardless of study sponsorship, this study is subject to monitoring by the Indiana University Simon Cancer Center Data Safety Monitoring Committee (DSMC). The DSMC chair and/or coordinator will review all expedited SAE reports through OnCore®. Expedited reports are completed per IRB guidelines and may include the IRB prompt reporting form, non-compliance form, AdEERS reports, MedWatch, and additional SAE forms as required by the sponsor. Submission of this information to the DSMC is additional to any other protocol-specified regulatory bodies (e.g., FDA, pharmaceutical company) to be notified. When follow-up information is received, a follow-up report should also be created in OnCore®. The DSMC chair and/or coordinator will review expedited SAE reports monthly and report findings to the DSMC quarterly.

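### The safety population is keyed to radiation, so an adverse event from a pre-treatment research scan in a subject who never starts radiation is left out of every safety table

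*Combined protocol and SAP*

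**What the plan says.** Section 13.3.2 sets the safety population: "The safety population comprises all subjects who have received at least one dose of radiation". It adds: "This set will be used for safety analysis".

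The safety paragraph of 13.7 contains three statements that matter here:

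- on listings: "Additionally, all safety data will be listed";
- on the incidence table: "For the treatment-emergent AEs, namely AEs started or worsened during the on-treatment period, the incidence will be summarized by system organ class";
- after the sentence on deaths and SAEs, on the population: "This will be done with the safety set".

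The start of the on-treatment period is not defined.

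Section 17.3 sets the start of collection: "Adverse events (AEs) will be recorded from the time of first study intervention and throughout the follow up period". The protocol does not say whether the first study intervention is a scan, the planning step or the first fraction.

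Section 9.2 lists two items as research imaging: the HIDA scan and "MRI with Eovist contrast of abdomen and pelvis". Section 8.2 and the study calendar (10.0) put both between consult and treatment. A scan from before the consult may be reused if it falls within 8 weeks of simulation (calendar note F), and a subject may be enrolled without the Eovist MRI (8.2).

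Section 13.3.1 defines an enrolled population, but no safety output is assigned to it.

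**The concern.** In most trials a treated-subjects safety set starts at the first study exposure. Here it need not. The subjects already plan to receive SBRT (6.0), and one of the two plans is the standard one (9.1). What the study adds is mainly the imaging and the plan built on it, and the first on-study scans come before the first fraction. The safety set is thus keyed to the background treatment and not to the first procedure the study adds.

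Membership also depends on something that happens after exposure and that the harm itself can influence. A serious reaction to a scan could be the reason why radiation is not started. The subject then leaves the set because of the event that the tables ought to show, so the omission is not random, and it can only make the tabulated burden of scan-related events look smaller.

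At stake is the completeness of the final safety report. Section 13.4 names as a possible next step a Phase I trial using HIDA- and functional-MRI-guided planning, including patients with poor liver function. Tolerability of the imaging is relevant background for that trial, though it is not a decision criterion in this one.

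**Working it through.** **The plan's own figure.** The only computed figure is the power table in 13.4. For 15 subjects and a true rate of 0.30,

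P(X ≥ 3) = 1 − Σ (x = 0 to 2) C(15, x) · 0.30^x · 0.70^(15 − x) = 0.873,

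against the stated 0.87. The entries for 0.1, 0.2, 0.25, 0.4 and 0.5 come out at 0.184, 0.602, 0.764, 0.973 and 0.996, matching 0.18, 0.60, 0.76, 0.97 and ≥ 0.99. None of these uses the safety set, so the 3-of-15 rule is unaffected.

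**Where a scan event before radiation goes.** Suppose first that an on-study scan counts as study intervention, so that the event is recorded under 17.3.

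| Subject | On-treatment period starts at the scan | On-treatment period starts at fraction 1 |
|---|---|---|
| Later irradiated | In the AE incidence table | Not in the AE incidence table; if serious, still in the SAE tabulation, which is not limited to treatment-emergent events |
| Never irradiated | In no safety table | In no safety table |

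The bottom row follows from 13.3.2 and the closing safety-set sentence of 13.7, whichever way the period is defined. The top right cell depends on the undefined period.

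Suppose instead that the first study intervention means radiation. Then 17.3 does not require AE recording before the first fraction. The gap would lie in collection as well as analysis, and a change to 13.3.2 alone would not close it.

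**Size.** Inputs: 20 enrolled and 15 evaluable (13.4), so 20 − 15 = 5 subjects (5/20 = 25%) may be non-evaluable for any reason. The documents give neither the number of non-starters nor a scan AE rate. I assume k = 0 to 5 non-starters. The safety set as written then has 20 − k subjects. The redefined set has up to 20, and exactly 20 only if every non-starter had an on-study scan.

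1. *One serious scan event in a non-starter (illustration).* With k from 1 to 5, the tables show 0/19 to 0/15, that is 0%. The wider set gives 1/20 = 5%. With k = 0 nothing changes.
2. *Precision when no events are seen.* The one-sided 95% upper bound is 1 − 0.05^(1/n).

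| Non-starters k | n as written | Bound as written | Bound at n = 20 |
|---|---|---|---|
| 0 | 20 | 13.9% | 13.9% |
| 1 | 19 | 14.6% | 13.9% |
| 5 | 15 | 18.1% | 13.9% |

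3. *Chance that at least one event is missed.* If each scanned non-starter has an event with probability q, this is 1 − (1 − q)^k. For k = 1 to 5 it runs from 1% to 4.9% at q = 1%, from 5% to 22.6% at q = 5%, and from 10% to 41% at q = 10%. These values of q are assumptions. If a reaction can itself stop a subject from starting, q among non-starters is higher than among all scanned subjects.

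**The case against.** The best defence is that the set fits the stated safety objective. Section 4.2 asks about treatment toxicity, 4.5 specifies post-treatment changes in liver function tests and CTP score together with hepatic toxicities, and the monitored list in 11.0 has no contrast-reaction term. For those questions irradiated subjects are the right denominator. The plan names no estimate of harm from imaging, so no named endpoint is biased. This stands, and it is why the irradiated subset should be kept. It does not explain why scan-related AEs in non-starters should appear in no table, since 13.7 sets out to report AEs and SAEs generally.

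Three stronger readings are tempting and are not supported:

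- *Such events are collected and then vanish.* Collection depends on the undefined term in 17.3. Where they are recorded, the sentence that all safety data will be listed may fall outside the safety-set limit. DSMC and IRB reporting (16.0, 17.3) is not tied to the analysis set either. The supported claim concerns the final tables, not live oversight.
- *The plan expects 5 subjects to be scanned and not irradiated.* The allowance from 20 to 15 refers to having one-month follow-up and covers loss for any reason, including after radiation. It bounds a planning range and forecasts nothing about non-starters.
- *The protocol foresees serious reactions to the research scans.* Section 5.1 says "Subjects with an allergy to contrast agents may be enrolled", with pre-treatment and symptom management. That covers contrast in general: the simulation CT also uses IV contrast (9.3), and calendar note G gives CT contrast allergy as its example. This is weak support at most.

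Exposure is also narrower than all non-starters. Reused scans and omitted Eovist MRIs are not on-study exposures, and subjects who have the midway or follow-up HIDA scans after receiving radiation are already in the set.

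**Conclusion.** The point holds as a gap in the safety tables. Read together, 13.3.2 and 13.7 exclude from every safety table a subject who has an on-study research scan and never starts radiation, and the exclusion can be caused by the event itself. If the on-treatment period starts at fraction 1, pre-radiation scan events are missing from the AE incidence table for irradiated subjects as well.

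The size is minor to moderate. It is zero if every scanned subject starts radiation. Otherwise each affected subject is 1/20 = 5% of planned enrolment. This rests on the assumed range of 0 to 5 non-starters and on the non-starters having had an on-study scan. The power table, the 3-of-15 rule and the treatment-toxicity denominator are not in question.

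**What to change.** 1. In 13.3.2, define the safety population as all enrolled subjects with any on-study research scan (HIDA or Eovist MRI) or at least one fraction of radiation.
2. Keep the irradiated subset as a named denominator for radiation toxicity, so that the objective in 4.2 is analysed as now.
3. In 13.7, define when the on-treatment period starts, and summarise events with onset before fraction 1 in a separate table for all subjects in the new set.
4. In 17.3, state that the first study intervention includes the on-study research scans, so that these events are collected whether or not radiation follows.

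The cost is wording in three sections, one small extra table and possibly a little more AE recording before radiation. If the sites already treat the scan as the first study intervention, the recording cost is nil.

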13.3.3 Efficacy Population

The efficacy population comprises all subjects who have received at least one dose of radiation, and have been evaluated for the primary endpoint. This population will be used for efficacy analysis.

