4.4 Primary Endpoint

1. The functional reserve of liver will be calculated for both a plan that takes the HIDA scan into account and a plan that does not take this into account. The functional reserve will be calculated by (number of counts outside 15 Gy isodose line / total number of counts within the liver) * global liver function.

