8.2 Simulation Period

After subjects have been found eligible and enrolled to this study, each subject will undergo CT simulation for SBRT treatment planning. Two radiation treatment plans will be created for each subject and compared. The plan which best spares functional liver while maintaining adequate target coverage will be selected for each subject. Within 8 weeks of the simulation, the subject should have the following functional scans for enrollment:

1. HIDA scan
2. MRI with Eovist contrast (fMRI)

If a patient cannot obtain an MRI or refuses to undergo eovist MRI, the subject may be enrolled on the study at the discretion of the principal investigator.

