9.1 Overview

Each subject will have two radiation treatment plans created after enrollment and prior to start of radiation treatment during the simulation period. One treatment plan will follow the standard of care planning for SBRT. The second plan will incorporate functional data from the HIDA scan with the standard SBRT treatment plan. As per standard protocol, the 2 plans for a given subject will be evaluated by a dose-volume histogram to ensure SBRT constraints are met. A functional DVH will also be analyzed in order to allow a comparison of the potential relative sparing of function that the plan in which the functional data was accounted for provides.

In the HIDA-guided plan, the target will be identical and the dose to the target will not change compared with a conventionally planned SBRT plan. Tumor coverage will be equivalent between both plans. Although HIDA-guided SBRT planning may result in changes in the geometric beam arrangement and the relative weighting of beams in order to attempt to increase sparing of functional liver, HIDA-guided planning will not result in any changes to the delineated tumor target nor in the accepted level of dosimetric coverage of the tumor target itself.

[figure not shown]
The HIDA scan will be “fused” (overlaid) over the patient’s treatment planning CT, and contours that delineate areas of differing liver function will be created. The first step in contouring is the delineation of the tumor. An example of this can be found in Figure 1 below. The tumor is shown as the turquoise-colored volume in the posterior right lobe, and the liver is indicated by the dark blue contour. The HIDA scan data will then be utilized to create contours delineating areas of higher- and lower-functioning liver. The example in Figure 1 shows contours corresponding to liver function (i.e., % maximum uptake as depicted by the HIDA scan. Here, 25%-50% max (green), 50-75% max (yellow), 75-90% max (orange), 90-100% max (red). In this case, the left lobe of the patient’s liver was providing the majority of her liver function. Therefore, the HIDA scan suggests that the left lobe of the liver should be avoided, as segments 1-4 are shown to contribute more to liver function than the right lobe of the liver.

Figure 1. HIDA-guided Contouring

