13.6 Analysis of Primary Objective

The efficacy set will be used for all the efficacy analysis, unless otherwise noted. For the primary endpoint of difference of functional reserve of liver, the value will be calculated for each subject and described by basic summary statistics. The summary statistics will be displayed overall and by each plan chosen.

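### The efficacy set requires a radiation dose, so subjects with both plans complete who are never irradiated leave the primary and plan-choice analyses, though neither result uses delivered dose

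*Combined protocol and SAP*

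**What the plan says.** Section 13.3.3 defines the efficacy population as "all subjects who have received at least one dose of radiation, and have been evaluated for the primary endpoint". Section 13.6 adds: "The efficacy set will be used for all the efficacy analysis, unless otherwise noted". No exception is noted there for the primary endpoint, or in 13.7 for the plan-choice rate, where "The rate at which the plan that utilized the HIDA scan is chosen for the actual treatment will be summarized" with an exact 95% binomial interval and no stated denominator. The enrolled population in 13.3.1 is defined but given no analysis, and no listing of planned-but-untreated subjects is described.

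The timing of the planning results is clear:

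- Section 9.1: "Each subject will have two radiation treatment plans created after enrollment and prior to start of radiation treatment during the simulation period".
- Section 4.4: "The functional reserve of liver will be calculated for both a plan that takes the HIDA scan into account and a plan that does not". The formula uses HIDA counts outside the 15 Gy line, total liver counts and global liver function.
- Section 8.2, under the simulation period: "The plan which best spares functional liver while maintaining adequate target coverage will be selected for each subject".

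**The concern.** The primary objective compares two ways of planning, and the data that answer it are complete when planning ends. Requiring a later radiation dose adds a condition that the endpoint does not need. It removes observed data rather than handling missing data, so the no-imputation rule in 13.1 does not explain it.

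The exclusion takes effect after the planning result is known, so it can depend on that result. The protocol shows two routes. Under 9.1, "the 2 plans for a given subject will be evaluated by a dose-volume histogram to ensure SBRT constraints are met", and a subject for whom neither plan is acceptable might not be treated. Under section 12.0, the investigator or treating physician "may choose to withdraw a subject from the study if there are safety or other concerns". If subjects lost by either route differ in how much HIDA guidance helped them, both the benefit count and the plan-choice rate describe only those who went on to treatment.

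**Working it through.** **Inputs.** From 13.4: 15 evaluable subjects; benefit is a relative improvement of 5% or more in functional reserve; the rule is at least 3 of 15. The number planned but never irradiated is not given. I assume a loss L of 5% to 10% of planned subjects.

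**The plan's own figures.** P(X ≥ 3), with X ~ Binomial(15, p), is 0.1841, 0.6020, 0.7639, 0.8732, 0.9729 and 0.9963 at p = 0.1, 0.2, 0.25, 0.3, 0.4 and 0.5. This reproduces the table in 13.4, including the 87%.

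**Worst-case selection.** Let p be the true benefit rate among planned subjects, with 15 treated subjects analysed. The rate among treated subjects is:

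- p/(1 − L) if every lost subject had no benefit;
- (p − L)/(1 − L) if every lost subject had benefit.

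For example, with p = 0.30 and L = 0.10, the second formula gives 0.20/0.90 = 0.2222, and P(X ≥ 3) = 0.6805.

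| True p | L | Rate, lost had no benefit | P(pass) | Rate, lost had benefit | P(pass) |
|---|---|---|---|---|---|
| 0.10 | 0 | 0.1000 | 0.1841 | 0.1000 | 0.1841 |
| 0.10 | 5% | 0.1053 | 0.2047 | 0.0526 | 0.0412 |
| 0.10 | 10% | 0.1111 | 0.2283 | 0 | 0 |
| 0.30 | 0 | 0.3000 | 0.8732 | 0.3000 | 0.8732 |
| 0.30 | 5% | 0.3158 | 0.8979 | 0.2632 | 0.7976 |
| 0.30 | 10% | 0.3333 | 0.9206 | 0.2222 | 0.6805 |

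These are bounds. Loss unrelated to the planning result leaves the rate among treated subjects equal to p and costs only precision.

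**Plan choice (hypothetical counts).** Suppose the HIDA plan is used in 10 of 15 treated subjects: 66.7%, exact 95% interval 38.4% to 88.2%. Add two planned-but-untreated subjects. The rate lies between 10/17 = 58.8% (HIDA plan selected for neither) and 12/17 = 70.6% (selected for both). With five added, it lies between 10/20 = 50% (27.2% to 72.8%) and 15/20 = 75% (50.9% to 91.3%).

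**Threshold after the change.** The denominator could exceed 15, so the rule has to change with it:

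| Rule | P(pass), p = 0.10 | P(pass), p = 0.30 |
|---|---|---|
| 3/15 (current) | 0.184 | 0.873 |
| 3/20 | 0.323 | 0.965 |
| 4/20 | 0.133 | 0.893 |
| 4/16 | 0.068 | 0.754 |

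Keeping the cut at 3 with 20 subjects makes the rule easier to pass when the true rate is low. Moving to 4 with only 16 subjects costs power at 30%.

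**The case against.** The best defence is that few subjects should be lost this way and that little depends on them. Eligibility is narrow: CTP score at most 7, no more than three lesions, and a summed diameter of at most 6 cm. The background says standard constraints will be met, 9.4 offers IMRT when they are not, and 8.2 expects a plan to be selected for every subject. The comparison is within subject, so dropping someone removes both values and distorts no remaining contrast. The analysis is descriptive, in a pilot whose rule only encourages further study. The plan-choice endpoint is worded around the plan actually used for treatment, so a treated-only denominator is a natural reading.

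Most of this stands as a limit on size. It does not explain why complete primary data should be discarded, and it leaves the plan-choice denominator unstated.

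Three stronger readings are tempting and not supported:

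- **That up to 5 of 20 subjects will be lost before treatment.** Section 13.4 ties the 15 to having one month of follow-up. A subject lost after irradiation who has the primary endpoint stays in the efficacy set.
- **That subjects with little reserve or failed constraints are the ones left untreated.** No section says so; the routes are possible, not documented.
- **That the plan-choice rate is inflated.** A subject whose HIDA plan was selected and who then withdrew would raise the rate once counted.

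**Conclusion.** The point holds in limited form. As written, 13.3.3 and 13.6 discard complete primary-endpoint data from planned but unirradiated subjects and permit selection after the planning result is known. Neither the number of such subjects nor the direction of any bias can be taken from the documents. Under the assumed 5% to 10% loss, the adverse bounds are a modest rise in false encouragement at a true 10% rate (0.184 to at most 0.228) and a larger fall in power at a true 30% rate (0.873 to 0.80 or 0.68). Both require every lost subject to be of one kind. The 87% in 13.4 is arithmetically correct and is not in question. The change is worth making because it costs almost nothing and removes a condition that the endpoint does not need.

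**What to change.** - In 13.3, add a planning population: all eligible registered subjects with both plans and a usable pre-treatment HIDA scan, irradiated or not. Use it for the primary endpoint in 13.6, and keep the current efficacy set as a sensitivity analysis.
- In 13.4, restate the benefit rule for the resulting denominator with its operating characteristics, over the range of numbers that could occur. State whether the one-month follow-up condition applies to this rule; the planning endpoint does not need it.
- In 13.7, count each planned subject by the plan selected under 8.2, with 'neither plan acceptable' as its own category within the denominator. Do not code every untreated subject as not choosing the HIDA plan, because that misclassifies those for whom it was selected. Also report the rate among treated subjects.
- List planned-but-untreated subjects with reasons.
- Keep the at-least-one-dose condition for safety, LC, PFS, OS and post-treatment function, where it is appropriate.

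The cost is a change of wording and a recomputed threshold. The data already arise from planning. The plan-choice rate may move slightly in either direction.
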